## 6.2 SAFETY ENDPOINTS

- **Primary Safety Endpoint**
  - Procedure (TearCare)/Treatment (Restasis)-related adverse events (all adverse events will be recorded)
- **Secondary Safety Endpoints**
  - Change in best corrected visual acuity (ETDRS)
  - Change in intraocular pressure (IOP)

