# **10 ADVERSE EVENTS (AES)**

Adverse Events are defined below. Adverse events that occur in the eye during the trial, whether considered to be device related or not, must be documented in the subject’s records. Non-ocular adverse events do not need to be recorded as adverse events unless they meet the definition of serious adverse event or are believed to be related to the study device or a study procedure. Date of the event, its severity, treatment (if any), and the assessed relationship of the event to the study device will be recorded on the Adverse Event Form. Conditions which exist at the time the subject is enrolled will be considered pre-existing conditions and do not need to be recorded as adverse events unless they increase in severity during the study.

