## **12.6 SAFETY ENDPOINTS AND ANALYSIS**

### **12.6.1 DESCRIPTIVE ANALYSES**

All adverse events, changes in IOP, and changes in BCVA (EDTRS) will be tabulated by visit and study group.

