### **12.6.4 SAFETY ANALYSIS**

All adverse events will be reported by study group and AE category. Any serious adverse events will be completely described in the study report. The primary safety endpoint will be summarized for each study group.

We will compute the incidence of ocular events in two ways: first as a simple proportion, counting the number of subjects with any event (that is, counting the first event per person in either eye), then as an incidence rate, counting all events including repeated events per subject.

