## **22.6 SAFETY ANALYSIS**

All adverse events will be reported by treatment group and AE category. Any serious adverse events will be completely described in the study report. The primary safety endpoint will be summarized for each treatment group.

We will compute the incidence of ocular events in two ways: first as a simple proportion, counting the number of subjects with any event (that is, counting the first event per person in either eye), then as an incidence rate, counting all events including repeated events per subject.

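### Section 6.2 says all adverse events are recorded and the plan promises tables of them, but Section 10 lets sites leave out non-serious non-ocular events not thought related

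*Combined protocol and SAP*

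**What the plan says.** Section 6.2 defines the primary safety endpoint as adverse events related to the TearCare procedure or to Restasis treatment, and adds in parentheses that "all adverse events will be recorded".

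The analysis sections carry the same scope:
- Section 12.6.1: "All adverse events, changes in IOP, and changes in BCVA (EDTRS) will be tabulated by visit and study group".
- Section 12.6.4: "All adverse events will be reported by study group and AE category".
- SAP Section 22.6: "All adverse events will be reported by treatment group and AE category".

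Section 10 sets the recording rule for sites. For ocular events it is complete: "Adverse events that occur in the eye during the trial, whether considered to be device related or not, must be documented". For other events it is not: "Non-ocular adverse events do not need to be recorded as adverse events unless they meet the definition of serious adverse event", or unless they "are believed to be related to the study device or a study procedure". Nothing in the current text reconciles this with Section 6.2.

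**The concern.** A site that follows Section 10 does not deliver what Section 6.2 states. For a non-serious non-ocular event, the opinion on cause decides whether the event has to be recorded at all, and not only how it is classified. An event that was never recorded cannot be re-attributed later or counted in an any-cause summary.

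A reader of the final report who sees a table of all adverse events would take a low non-ocular count as an observation about safety. It might instead reflect the recording rule. Because the rule permits omission without requiring it, sites could also differ in how much they record.

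**Working it through.** **1. Recording scope, by type of event**

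| Type of event | Section 6.2 | Section 10 | Agree? |
|---|---|---|---|
| Ocular, any cause | recorded | recorded | yes |
| Serious non-ocular, any cause | recorded | recorded | yes |
| Non-serious non-ocular, thought related to device or study procedure | recorded | recorded | yes |
| Non-serious non-ocular, thought related to Restasis | recorded | Restasis not named; optional if read literally | unclear |
| Non-serious non-ocular, thought unrelated | recorded | optional | no |

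The clear conflict is in the last row. The fourth row is a gap in wording. Section 7.1 makes the TearCare System the study device and Restasis the control. Section 10.3 asks only for the relationship to the study device, and the adverse event definition in Section 10.1 refers to subjects treated with the device. The drops might be meant to fall under study procedure, but no section says so.

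**2. Who makes the judgement**

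Section 10.3 gives adverse event reporting to the principal or designated investigator. Section 4.1 has the investigator perform the TearCare procedure, and Section 9.9 bars Masked Assessors from performing it or distributing Restasis. Adverse event assessment has no masked-assessor asterisk in Section 9.6.2 and is not on the masked list in Section 9.9. Subjects are unmasked (Section 7). It follows that the relatedness opinion is probably unmasked. That is an inference; no section states it.

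**3. What the planned outputs use**

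The tables in 12.6.1, 12.6.4 and 22.6 are descriptive, with no between-group test. The incidence calculation is restricted: "We will compute the incidence of ocular events in two ways". Its inputs are ocular events, which Section 10 captures in full.

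**4. The plan's own safety figure**

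Section 22.4.2 gives margins of error of 4.4%, 6.0% and 8.1% for event rates of 5%, 10% and 20% with 98 TearCare subjects. Using t(0.975; 97) × √(p(1−p)/97), with t = 1.9847:
- p = 5%: 1.9847 × √(0.0475/97) = 4.39%
- p = 10%: 1.9847 × √(0.09/97) = 6.05% (6.0455% before rounding)
- p = 20%: 1.9847 × √(0.16/97) = 8.06%

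The stated figures are reproduced. They describe sampling error in the recorded rate. For an event type that sites may leave out, they say nothing about how far the recorded rate lies below the true one.

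**5. Size**

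The documents give no non-ocular rate, so the following rests on assumed rates. With 155 subjects per arm (Section 22.4.1) and an assumed true incidence of 2% to 30%, between 155 × 0.02 = 3.1 and 155 × 0.30 = 46.5 subjects per arm would have a non-serious non-ocular event. This is a ceiling on the loss, reached only if every such event were judged unrelated and left out.

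To show what the rule permits, assume a true rate of 20% in both arms, 30% of events judged related under TearCare and 10% under Restasis, and every optional event left out:
- TearCare: 0.20 × 0.30 = 6% recorded (155 × 0.06 = 9.3 subjects)
- Restasis: 0.20 × 0.10 = 2% recorded (155 × 0.02 = 3.1 subjects), or 0% if events attributed to Restasis fall outside the rule

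Over true rates of 10% to 30% and related shares of 10% to 30% (TearCare) and 0% to 10% (Restasis), recorded rates run from 0.10 × 0.10 = 1% to 0.30 × 0.30 = 9%, and from 0% to 0.30 × 0.10 = 3%. No figure in the documents says where in these ranges the trial would fall.

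**The case against.** The strongest reply is that Section 10 defines what counts as a recorded adverse event, and that the tables in 12.6 and 22.6 simply show all events so recorded. On that reading only the parenthesis in 6.2 is wrong. Restricted collection of non-ocular events is also a choice that the protocol states openly. The listed anticipated events in Section 10.2 are ocular or eyelid events, and the primary safety endpoint is based on relatedness, so leaving out events judged unrelated does not change it.

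Most of this stands, and it limits the point. It does not remove the conflict. The analysis sections do not say that their tables follow the restricted rule, and 6.2 says the opposite.

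A reader might infer more than the text supports, in three ways:
- That Section 10 forbids recording these events. It only makes recording optional, so an unrelated event may be missing but need not be.
- That a planned comparison of all adverse events between arms is biased by unmasked opinion. No such comparison is tested, and it is only inferred that the person assessing relatedness is unmasked.
- That 6.2 promises any-cause recording as a check on the relatedness endpoint. It states no such purpose.

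**Conclusion.** The inconsistency is in current text and should be corrected. Its reach is narrow: non-serious non-ocular events, in descriptive tables. For those events the plan claims complete recording that its own collection rule does not ensure, so any-cause non-ocular incidence cannot be read from the tables.

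The size of the loss is unknown, and the counts above depend wholly on assumed rates. The documents do not show that the primary safety endpoint is biased. One part does touch that endpoint: because Sections 10 and 10.3 do not name Restasis, it is unclear whether a non-serious non-ocular event attributed to the drops must be recorded, although 6.2 counts it.

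**What to change.** Reconcile Sections 6.2, 10, 10.3, 12.6 and 22.6 in one of two ways.

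(a) Change Section 10 so that every adverse event in both arms is recorded, ocular or not and whatever its judged cause, for the full follow-up. Tables 3 and 4 already schedule an adverse event assessment at every visit, to Month 24 for TearCare and Month 12 for the Restasis group including crossover. Section 22.5.1 already plans MedDRA coding. The cost is extra entries and coding. The change cannot recover earlier events. Section 12.7 shows that subjects had already been treated by May 2021, so the report should state the date of the change and which recording rule applied before it.

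(b) Keep the restriction and delete "all adverse events will be recorded" from Section 6.2. Label the tables in 12.6.1, 12.6.4 and 22.6 as all ocular adverse events, all serious adverse events, and non-ocular adverse events judged related. State that any-cause non-ocular incidence cannot be estimated. The relatedness wording in Sections 10 and 10.3 must then name Restasis as well as the device and study procedures. Otherwise neither the new label nor the primary safety endpoint in 6.2 would hold in the control arm. The cost is wording and a narrower safety claim.

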## 7 STUDY DESIGN

This is a prospective, randomized, masked, multi-center, superiority, non-significant risk study. To reduce potential bias in the study, study staff performing the endpoint assessments will be masked as to the subject's treatment allocation. Subjects cannot be masked as it will be obvious to them which treatment they are receiving.

### 7.1 STUDY DEVICE AND CONTROL GROUP

In this study, TearCare procedures using the TearCare System (study device) will be compared with Restasis (control group).

TearCare procedures in this study will include an in-office eyelid debridement, 15-minute bilateral thermal session with the TearCare System, immediately followed by manual expression of the meibomian glands using the Clearance Assistant Plus device. Subjects randomized to TearCare will receive one in-office TearCare procedure within 7 days of the Baseline visit and at 5 Months. Beginning at 9 Months, subjects will receive an additional TearCare procedure when TBUT drops lower than Baseline or within 2 seconds of baseline AND if OSDI worsens by at least 15 points compared to the previous visit.

Subjects randomized to Restasis group will be required to self-administer 1 drop twice a day from baseline through the Month 6 visit. At Month 6, subjects will be crossed over to the TearCare group and will receive one (1) TearCare procedure.

### 7.2 STUDY CENTERS

This study will be conducted at up to 25 centers in the United States. No center will have more than 20% of the target enrolled and treated (i.e., 70 subjects per site) without prior approval from the sponsor.

## 8 STUDY SELECTION CRITERIA

### 8.1 INCLUSION CRITERIA

For inclusion in this study, subjects must meet all of the following criteria:

1. At least 22 years of age
2. Reports dry eye symptoms within the past 3 to 6 months
3. Reports having to use artificial tears or lubricants regularly over the past month to relieve dry eye symptoms.
4. Schirmer tear test (with anesthesia)  $\geq 5$  to  $\leq 15$  mm in 5 minutes
5. OSDI Score of 23-79
6. TBUT of  $\geq 1$  to  $\leq 7$  seconds in both eyes
7. Meibomian gland obstruction in both eyes based on a total Meibomian Gland Secretion Score  $\leq 12$  in each eye.
8. At least 15 glands in each lower eyelid should be expressible, with a sterile cotton swab, at the slit lamp.
9. Best corrected visual acuity of 20/100 or better in both eyes.
10. Willing and able to comply with the study procedures and follow-up
11. Willing and able to provide informed consent
12. English-speaking

### 8.2 EXCLUSION CRITERIA

A subject who meets any of the criteria listed below (in either eye) will be excluded from the study:

1. Use of any of the following medications:
  - a) Cyclosporine (Restasis, Cequa etc.) or Xiidra and serum tears within 60 days prior to baseline;
  - b) Antihistamines (oral or topical) within 7 days prior to baseline;
  - c) Systemic medication(s) that is known to cause ocular dryness (e.g. diuretics, anti-hypertensives, anti-depressants, antihistamines, hormone therapy) and whose dose of this medication(s) has not been stable within 30 days prior to baseline. There must be no anticipated adjustments to the dose of these medications for the duration of the trial;
  - d) Accutane (at any time);
  - e) Oral tetracyclines or azithromycin within 30 days prior to baseline; or
  - f) Topical ophthalmic antibiotics, anti-glaucoma medications, steroids, non-steroidal anti-inflammatory medications within 30 days prior to baseline.

2. Any of the following dry eye treatments:
  - a) Office-based dry eye treatment (e.g. IPL, TearCare, thermal pulsation [LipiFlow], iLux etc.) within 12 months prior to baseline either as part of routine care or clinical investigation;
  - b) Planned or recent surgical procedures to the eye or eyelid (90 days prior to baseline)
  - c) Meibomian gland expression within 6 months prior to baseline;
  - d) Blephex or debridement within 3 months prior to baseline is an exclusion;
  - e) Punctal occlusion or punctal plug Punctal occlusion or punctal plugs. Investigators can choose to remove the punctal plugs 15 days prior to baseline;
  - f) Use of tear neurostimulators (i.e., True Tear, iTear100, Tyrvaya) within 2 weeks of the baseline visit. (Subjects must refrain from using tear neurostimulators for the duration of the study.); or
  - g) Any history of meibomian gland probing
3. History of eyelid, conjunctiva, or corneal surgery (including refractive surgery) within the past year prior to baseline. In addition, subjects with any history of the following are excluded: chalazion surgery, surgery on the tarsal conjunctiva, radial keratotomy(RK), complicated blepharoplasty, lid reconstruction, or significant complications post-refractive surgery.
4. Contact lens use within 2 weeks of the baseline visit.
5. Active hordeolum, stye, or chalazion at the time of the baseline visit.
6. History of Herpes Simplex or Herpes Zoster of the eye or eyelid.
7. Any active, clinically significant ocular or peri-ocular infection, inflammation, or irritation
8. Recurrent clinically significant eye inflammation, other than dry eye, within 3 months prior to baseline
9. Clinically significant anterior blepharitis. In addition, collarettes or flakes of more than one quarter of the eyelid are excluded.
10. Clinically significant eyelid abnormalities in either eye (e.g. entropion/ectropion, blepharospasm, aponeurotic ptosis, lagophthalmos, distichiasis, trichiasis).
11. Clinically significant dermatologic or cutaneous disease of the eyelid or periocular area.
12. In the clinical judgement of the investigator, meibomian glands have significant capping, atrophy, or are unable to be expressed, digitally or with a sterile cotton swab.
13. Clinically significant ocular surface abnormalities that may affect tear film distribution or treatment (e.g. pterygium, anterior membrane dystrophy, Salzmann's nodules, etc.)

14. Corneal surface abnormalities such as corneal epithelial defects (other than punctate staining), ulcers, corneal epithelial dystrophies, keratoconus, and ectatic disease of the cornea
15. Any active, clinically significant allergic, vernal, or giant papillary conjunctivitis.
16. Ocular trauma within 3 months prior to baseline.
17. Known history of diminished or abnormal facial, periocular, ocular, or corneal sensation
18. Systemic diseases resulting in dry eye (e.g., autoimmune diseases such as Sjogren's syndrome, rheumatoid arthritis, lupus, Graves' disease, sarcoidosis, etc.)
19. Subject is currently using Retin A/Retin A derivatives.
20. Subject has permanent eyeliner/lid tattoos, eyelash extensions or wears false eyelashes.
21. Subject is currently using Latisse, Lash Boost or any other type of eyelash growth serum.
22. Allergies to silicone tissue adhesives, acrylates and/or coppers.
23. Subject has a pacemaker or implantable cardiac defibrillators (ICD). Participation in another ophthalmic clinical trial 30 days prior to baseline. Subject must also be willing to refrain from another ophthalmic study for the duration of the study.
24. Co-existing condition, either ocular or non-ocular that, in the judgement of the investigator could affect the safety or effectiveness of treatment or the compliance of the subject to the protocol. For example, subjects who are pregnant or nursing or have active, wet macular degeneration are excluded.

## 9 STUDY PROCEDURES

### 9.1 TABLE 3: TEARCARE STUDY VISIT SCHEDULE

Visit	Baseline	Day 0 b	Day 1	Wk 1	1 M	3 M	5 M	6 M	9 M	12 M	15 M	18 M	24M
Window days	-7 to 0	0	1	5-9	21-35	70-100	120-155	170-210	250-300	330-390	420-480	510-570	691-780
Informed Consent	X a												
Demographics, Ocular & Medical History	X												
Medication use	X			X	X	X		X	X	X	X	X	X
Questionnaires (OSDI, SANDE, Eye Dryness Score)	X			X	X	X		X	X	X	X	X	X
BCVA d	X		X e	X e	X	X		X	X	X	X	X	X
Blink rate	X			X				X		X			X
Slit Lamp Exam	X		X	X	X	X		X	X	X	X	X	X
TBUT	X			X	X	X		X	X	X	X	X	X
Corneal Staining	X			X	X	X		X	X	X	X	X	X
Conjunctival Staining	X			X	X	X		X	X	X	X	X	X
Schirmer Test	X			X	X			X		X			X
MGSS	X			X	X	X		X	X	X	X	X	X
IOP f	X		X	X	X	X		X	X	X	X	X	X
Subject Eligibility	X												
Randomization	X												
TearCare Procedure		X					X						
AE Assessment	X	X	X	X	X	X	X	X	X	X	X	X	X
Eye Lubricant/Drop Log				X	X	X	X	X	X	X	X	X	X

a Subjects may sign the informed consent up to 60 days in advance of the baseline visit.

b TearCare procedure must be performed within 7 calendar days of the Baseline visit. If scheduling permits, it may be performed on the same day as the Baseline visit following Randomization. Beginning at 9 Months, subjects will receive an additional TearCare procedure when TBUT drops lower than Baseline or within 2 seconds of baseline AND ifOSDI worsens by at least 15 points compared to the previous visit.

d BCVA should be collected after manifest refraction using ETDRS visual acuity chart

e On Day 1 and Week 1, Best Corrected Spectacle Visual Acuity (BCSVA using ETDRS) is measured without manifest refraction (MR). If the VA has worsened by  $\geq 10$  letters (per ETDRS) from baseline, then MR should be performed, the ETDRS measurement should be repeated, and the VA post-MR should be recorded.

f IOP measured via applanation tonometry should be measured at baseline using standard of practice at each site with the same method to be used for all consecutive visits in the study.

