Device related ocular adverse events were reported in two subjects (loss of visual acuity) for the TearCare® group and three subjects (loss of visual acuity, corneal abrasion and foreign body sensation) for the LipiFlow® group.

Figure 5: TBUT, MGSS, Corneal and Conjunctival staining per follow up time point. Blue legends, line and bars represent TearCare group and red legends, line and bars represent LipiFlow group.

[figure not shown]
[figure not shown]

Figure 6: SANDE, EDS and OSDI scores per follow up time point Blue legends, line and bars represent TearCare group and red legends, line and bars represent LipiFlow group.

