## 9.2 TABLE 4: RESTASIS STUDY VISIT SCHEDULE

Restasis								Restasis CROSSOVER to TearCare					
Visit	Baseline	Day 0	Day 1	Wk 1	1 M	3 M	6 M/TearCare	Post Procedure			9 M	12 M	
Window days	-7 to 0	0	1	5-9	21-35	70-90	150-180	Day 1	Wk 1	1 M	220-280	320-390	
								1	5-9	21-35			
Informed Consent a	X												
Demographics, Ocular & Medical Hx	X												
Medication use	X			X	X	X	X		X	X	X	X	
Questionnaires (OSDI, SANDE, Eye Dryness Score)	X			X	X	X	X		X	X	X	X	
BCVA b	X		X c	X c	X	X	X	X c	X c	X	X	X	
Blink rate	X			X			X		X			X	
Slit Lamp Exam	X		X	X	X	X	X	X	X	X	X	X	
TBUT	X			X	X	X	X		X	X	X	X	
Corneal Staining	X			X	X	X	X		X	X	X	X	
Conjunctival Staining	X			X	X	X	X		X	X	X	X	
Schirmer Test	X			X	X		X		X	X		X	
MGSS	X			X	X	X	X		X	X	X	X	
IOP d	X		X	X	X	X	X	X	X	X	X	X	
Subject Eligibility	X												
Randomization	X												
Restasis (1gtt BID)		X	X	X	X	X							
AE Assessment	X	X	X	X	X	X	X	X	X	X	X	X	
Crossover and TearCare Procedure							X						
Treatment preference questionnaire												X	
Eye Lubricant/Drop Log					X	X	X		X	X	X	X	

a Subjects may sign the informed consent up to 60 days in advance of the baseline visit.

b Restasis must be dispensed within 7 calendar days of the Baseline visit. If scheduling permits, it may be dispensed on the same day as the Baseline visit following Randomization.

c BCVA should be collected after manifest refraction using ETDRS visual acuity chart

d On Day 1 and Week 1, Best Corrected Spectacle Visual Acuity (BCSVA using ETDRS) is measured without manifest refraction (MR). If the VA has worsened by  $\geq 10$  letters (per ETDRS) from baseline, then MR should be performed, the ETDRS measurement should be repeated, and the VA post-MR should be recorded.

e IOP measured via applanation tonometry should be measured at baseline using standard of practice at each site with the same method to be used for all consecutive visits in the study.

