### **12.6.3 SECONDARY SAFETY ENDPOINTS**

The secondary safety endpoints include:

- Change in best corrected visual acuity (ETDRS)
- Change in intraocular pressure (IOP)

These endpoints will be summarized by treatment group and visit.

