In order to provide standardized and well-controlled assessment of visual acuity, all visual acuity assessments for a subject should be performed consistently (e.g., the same lighting conditions, viewing distance, etc.) at each visit.

*Recording and Scoring Best-Corrected Visual Acuity*

Using the Visual Acuity Worksheet, circle each letter the subject identifies correctly, write total correct for each row in the place provided, and compute the total correct for all rows. Do not mark letters read incorrectly or not read at all. Each letter read correctly is recorded as one. Only move to the next line if 4 or more letters are read correctly. If 3 or more letters are read correctly in the final line, then that line is used for the Snellen equivalent and the visual acuity score. If 2 or fewer letters are read correctly in the final line, letters read from that line are added to the total visual acuity score and the previous line is used for the Snellen equivalent.

The number of correct letters will be recorded on the study worksheets and entered into the EDC. For the Day 1 Visual Acuity measurement, if two measurements are made,

one BSCVA and one with manifest refraction, the latter VA obtained with manifest refraction should be entered into the EDC.

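### Day 1 and Week 1 acuity tables will mix refracted and unrefracted readings, chosen by the size of the loss, and the first reading is not kept in the database

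*Combined protocol and SAP*

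**What the plan says.** Change in best corrected acuity is a secondary safety endpoint (sections 6.2 and 12.6.3). It is purely descriptive: "All adverse events, changes in IOP, and changes in BCVA (EDTRS) will be tabulated by visit and study group" (12.6.1). No rule says how a repeated reading is handled in those tables.

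At baseline and from Month 1 onward, acuity is taken after manifest refraction (Table 3, footnote d; Appendix A, 21.2). On Day 1 and Week 1, acuity "is measured without manifest refraction (MR"). If it is 10 or more letters worse than baseline, the eye is refracted and re-read, "and the VA post-MR should be recorded" (Table 3, footnote e). Gains and smaller losses trigger nothing.

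Appendix A, 21.2 states the same procedure for all subjects. Its recording paragraph adds that when both readings exist, "the latter VA obtained with manifest refraction should be entered into the EDC". That sentence is written for the Day 1 measurement; Week 1 is not named.

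In Table 4 (control arm and crossover), the BCVA row carries marker b, whose text concerns dispensing Restasis. The Day 1 and Week 1 cells, including those after the crossover procedure, carry marker c: "BCVA should be collected after manifest refraction using ETDRS visual acuity chart". The IOP row carries d, whose text is the Day 1 and Week 1 acuity rule. Footnote e, the IOP text, has no marker in the table.

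**The concern.** A re-measurement triggered only by a bad result is one-sided. An eye must cross the 10-letter line twice to be counted, while an eye just short of it is never rechecked. The trigger is also the size of loss listed as an anticipated adverse event (section 10.2), so the rule acts exactly where the count is taken.

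Day 1 and Week 1 are the visits closest to the procedure. Corneal deformation is on the anticipated list. A refractive change of that kind is what a new refraction corrects, so it would not appear in the acuity tables. The prior comparative trial gives some reason to look: "Device related ocular adverse events were reported in two subjects (loss of visual acuity) for the TearCare® group" (5.2.4). The same sentence reports loss of acuity in the comparator group too and gives no timing, so it shows interest in the outcome rather than an early signal.

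The eyes that are not re-read are a separate problem. They carry an unrefracted reading compared with a refracted baseline, which can make average acuity look worse than it is.

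**Working it through.** The plan gives no figure to reproduce here. The first step sets the texts side by side; the second shows direction and rough size under stated assumptions.

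**Which reading reaches the table**

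- Baseline and Month 1 onward: refracted.
- Day 1 and Week 1, loss under 10 letters or any gain: unrefracted.
- Day 1 and Week 1, loss of 10 letters or more: refracted repeat, replacing the first reading. The replacement is explicit for the EDC at Day 1; for Week 1 it rests on the table footnotes.

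**Model.** All values are in letters. Baseline is b ~ N(0, s²), the unrefracted reading is u ~ N(−L − p, s²), and the refracted repeat is m ~ N(−L, s²), with independent errors. L is the true loss in best corrected acuity and p the mean number of letters lost by not refracting. Neither s nor p is in the documents; s = 2, 3.5, 5 and p = 0, 2, 4 are assumed. Letters are treated as continuous. The recorded change is m − b if u − b ≤ −10, otherwise u − b. There were 2,000,000 simulated eyes per scenario.

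**Checks by formula**

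- With refraction for all, the share with a 10-letter loss is Φ((L − 10)/(s√2)). For L = 0 and s = 3.5: Φ(−10/4.95) = Φ(−2.02) = 2.2%.
- Under the plan, both changes must be ≤ −10. They share b, so their correlation is 0.5. For L = 10 and p = 0: 1/4 + arcsin(0.5)/(2π) = 1/4 + 1/12 = 33.3%, against 50% with refraction for all.

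**Eyes recorded with a loss of 10 or more letters (%)**

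| True loss L | s | Plan's rule, p = 0 / 2 / 4 | MR for all |
|---|---|---|---|
| 0 | 2 | 0.00 / 0.00 / 0.01 | 0.02 |
| 0 | 3.5 | 0.38 / 0.68 / 1.08 | 2.17 |
| 0 | 5 | 2.30 / 3.23 / 4.21 | 7.9 |
| 10 | 2 | 33.3 / 44.4 / 48.9 | 50.0 |
| 10 | 3.5 | 33.3 / 40.5 / 45.4 | 50.0 |
| 10 | 5 | 33.3 / 38.5 / 42.7 | 50.0 |
| 15 | 2 | 93.1 / 95.7 / 96.1 | 96.1 |
| 15 | 3.5 | 74.9 / 80.2 / 82.8 | 84.4 |
| 15 | 5 | 63.3 / 68.3 / 71.8 | 76.0 |

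At L = 0 and s = 3.5 the count falls by 2.17 − 1.08 = 1.09 to 2.17 − 0.38 = 1.79 percentage points. With 155 subjects per arm (310 eyes; SAP 22.4.1) that is 3.4 to 5.5 eyes per visit. With 175 (350 eyes; section 9.3) it is 3.8 to 6.3. These eyes have no true loss, so what is removed is measurement noise.

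**Loss that refraction corrects.** At L = 0, p = 4, s = 3.5, 11.3% of eyes are 10 letters down before refraction and 1.1% are recorded so. The difference is not visible in the acuity tables.

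**Mean recorded change, s = 3.5**

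- L = 0: +0.13, −1.63 and −3.08 letters for p = 0, 2 and 4, against 0 with MR for all. For p = 2 or 4 the average loss is overstated.
- L = 10: −9.01, −9.78 and −10.13, against −10. For p = 0 or 2 it is understated.

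**Table 4 read literally.** If every control eye were refracted while TearCare eyes followed Table 3, with L = 0 and s = 3.5 the 10-letter count would be 2.2% in controls and 0.4–1.1% in TearCare. For p = 2 or 4 the TearCare mean would be the worse one. Neither difference would come from treatment.

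**The case against.** The strongest reply is that the post-refraction value is the endpoint. The endpoint and the listed adverse event are both defined on best corrected acuity, and baseline is refracted. Repeating an apparent 10-letter loss with refraction therefore confirms it on the baseline scale. This stands, and it rules out a stronger reading that a reader might infer, namely that early acuity loss is trimmed from the safety tables. A loss that remains after refraction is recorded, and in the table above most 15-letter losses survive.

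A reader might also infer from Table 4 that the arms follow different refraction rules. The documents do not support that. Table 4's own footnote d repeats the Table 3 rule for Day 1 and Week 1, and Appendix A, 21.2 gives one rule for all subjects. The markers are an off-by-one lettering slip. What stands is that section 9.7 sends sites to both tables, so a site could follow the marker literally.

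Other routes for detection also exist. Slit lamp examination and adverse event assessment take place on Day 1 and Week 1 in both arms. Ocular events must be documented whether or not they are device related (section 10). The first reading may also survive on the site worksheet. These routes limit the harm, but they do not put the first reading into the database or separate the two kinds of reading in the tables.

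**Conclusion.** The point holds as a data-handling weakness in a descriptive secondary safety endpoint. On Day 1 and Week 1 the acuity summaries mix refracted and unrefracted values selected by the outcome. Counts of 10-letter loss near the threshold are lowered, refraction-correctable loss is invisible in the acuity tables, and mean change can err either way. Later visits and the effectiveness analyses are untouched.

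The size cannot be derived from the documents. The illustrations rest on assumed error SDs and no-refraction penalties, normal independent errors, and adherence to footnote e. With no true loss, the effect on the count ranges from almost nothing at an SD of 2 to 2.3–4.2% instead of 7.9% at an SD of 5. No between-arm bias follows from the rule as written; it would arise only if sites followed Table 4's misplaced markers. The improvement is cheap and worth making, but does not threaten the trial's conclusions.

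**What to change.** - Enter both readings in the EDC whenever refraction is triggered on Day 1 or Week 1, with a flag showing which was taken after MR.
- Tabulate by arm, for each of these visits, the unrefracted change for all eyes, the number with a loss of 10 or more letters before MR, and the number still at that loss after MR.
- Extend the EDC entry rule in Appendix A, 21.2 to Week 1.
- Reconcile Table 4's markers with its footnotes, so that both arms and the post-crossover Day 1 and Week 1 visits visibly follow one rule.

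The cost is one extra EDC field per eye at these visits, one extra safety table, and an editorial correction. No examination is added for participants. The early acuity table may look slightly less favourable.
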